## 3. STUDY DESIGN

## 3.1. General Description

This is a Phase IV, interventional, multicenter, open-label, multinational study with 2 study periods (a Run-in period of 4 weeks and an Assessment period of 12 weeks) to assess the efficacy and safety of the extemporaneous combination of NEB and RAM in reducing SBP and DBP in hypertensive patients uncontrolled by monotherapy.

The trial will be conducted in approximately 26 investigational clinical sites in Bulgaria, Poland, and Hungary.

The total study duration is 16 weeks including a Run-in period of 4 weeks and an Assessment period of 12 weeks.

Note: For the purpose of this study, uncontrolled BP is defined as sitting SBP/DBP  $\geq$ 130/80 mmHg in patients < 65 years old and SBP/DBP  $\geq$  140/80 mmHg in patients  $\geq$  65 years old.

## Screening Visit 1 (Week -4):

Hypertensive patients with SBP ranging from  $\geq$ 140 to  $\leq$ 179 mmHg and/or DBP ranging from  $\geq$ 90 to  $\leq$ 109 mmHg on treatment, for at least 30 days prior to screening, with NEB 5 mg or any other BB, or RAM 5 mg or any other ACE-i will be screened for eligibility (Visit 1). Patients that did not meet eligibility criteria will be considered as screening failures and will not be rescreened.

#### Run-in period from Visit 1 (Week -4) to Visit 2 (Week 0):

On the same day of the Screening Visit, eligible patients will enter a Run-in period, during which:

• Patients receiving NEB 5 mg or RAM 5 mg will continue the same therapy for 4 weeks.

Page 14 of 46

• Patients on any other BB will be assigned to monotherapy with NEB 5 mg while patients on any other ACE-i will be assigned to monotherapy with RAM 5 mg for 4 weeks. The study is designed in order to ensure that 1:1 ratio between patients in the NEB and RAM arms will be achieved.

## Assessment period from Visit 2 (Week 0) to Visit 5 (Week 12):

After 4 weeks (± 2 days) of the Run-in period of monotherapy (Week 0), BP will be further assessed at Visit 2.

Patients with uncontrolled BP levels (sitting BP  $\geq$  130/80 mmHg in patients < 65 years old/sitting BP  $\geq$  140/80 mmHg in patients  $\geq$  65 years old) at Visit 2, with adequate treatment adherence (ranging between 80% to 120%) and who did tolerate the treatment, will enter into the Assessment period and will be assigned to the extemporaneous combination of NEB/RAM 5/2.5 mg. Patients with controlled BP levels (sitting BP < 130/80 mmHg in patients < 65 years old/sitting BP < 140/80 mmHg in patients  $\geq$  65 years old) and/or who do not tolerate the treatment or have an adherence range below 80% or above 120%, will be withdrawn from the study (drop-out patients).

After 4 weeks  $\pm 2$  days in the Assessment period (Week 4), patients BP will be further evaluated at Visit 3:

[figure not shown]
patients with controlled BP levels (sitting BP < 130/80 mmHg in patients < 65 years old/sitting BP < 140/80 mmHg in patients  $\geq$  65 years old)) will continue the same extemporaneous combination, while patients with uncontrolled BP levels will be up-titrated from NEB/RAM 5/2.5 mg to NEB/RAM 5/5 mg for further 4 weeks  $\pm$  2 days.

After further 4 weeks  $\pm$  2 days (Week 8) the BP will be assessed again (Visit 4): controlled patients will continue the same extemporaneous combination, while uncontrolled patients:if on NEB/RAM 5/2.5 mg, will be up-titrated to NEB/RAM 5/5 mg for further 4 weeks  $\pm$  2 days (Visit 5, Week 12);

if on NEB/RAM 5/5 mg, will be up-titrated to NEB/RAM 5/10 mg for further 4 weeks  $\pm$  2 days (Visit 5, Week 12).

At the end of the Assessment period (12 weeks  $\pm$  2 days), at Visit 5, the antihypertensive effect of the extemporaneous combination (NEB/RAM 5/2.5 mg, NEB/RAM 5/5 mg or NEB/RAM 5/10 mg) will be evaluated.

To correctly evaluate the additional effect of the combination therapy, the number of patients with uncontrolled BP on NEB or RAM monotherapy needs to be balanced at Visit 2. To maintain a 1:1 ratio during the Assessment period, a cap of 110 patients for each treatment arm

Page 15 of 46

(i.e., NEB and RAM) will be included at Visit 2 to maintain a balanced number of uncontrolled patients entering the Assessment period for each drug.

The evaluation will be done every 50 patients. If the entrance in the Assessment period for 1 of the 2 tested drugs will deviate more than 5%, a corrective measure will be initiated: according to the enrolment site statistics, 1 or more sites will be informed to enroll a greater number of patients being treated with the least represented drug in the Assessment period.

A total number of 270 patients will be screened, to obtain at least 215 completed patients at the end of the study (Visit 5) who have at least baseline and Week 12 assessments with primary efficacy data. For the sample size justification refer to section 12.2 of study protocol version 3.0.

Sitting BP will be measured at all visits before blood sampling. Blood Pressure will be measured in both arms at the Screening Visit (Visit 1) to detect possible between-arm differences. Three BP measurements will be performed for each arm. The arm with the higher mean DBP will be identified at screening and will be used in all subsequent visits for BP assessment. Blood pressure measurements should be performed as nearly as possible within the same time frame of the day (7:00 a.m. to 12:00 p.m.), on the same arm, possibly by the same trained member of the site staff/personnel and using the same calibrated automated device, provided by the Sponsor, at each visit.

Patients should be seated comfortably in a quiet environment for 5 minutes before beginning BP measurements.

Three BP measurements will be recorded, 1 to 2 minutes apart, and additional measurements only if the first 2 readings differ by >10 mmHg. The mean of the 3 recordings in sitting position will be used as the BP value for that visit. All BP measurements during the treatment phase will be performed as through readings (i.e., 24 + 2 hours after the last drug intake) using the same calibrated automated device, provided by the Sponsor. Study medication should be taken on the same time every day during the study; except the days of site visits, when study medication should be taken at the study center after all assessments mentioned as per study flow chart. At Visit 1 (Week -4) and Visit 5 (Week 12), a 12-lead ECG will be performed.

Safety (AEs, SAEs) will be measured at all visits. Any patient having an ongoing AE or SAE at the last visit, will be followed-up for further 2 weeks through a phone call to check about the status of the AE/SAE.

Page 16 of 46

At any visit, in case of a clinically relevant laboratory test abnormality according to the Investigator's judgment, the patient will be contacted through a phone call within 24 hours.

[figure not shown]
#### 3.2. Schedule of Events

Schedule of events can be found in Section 2.2 of the protocol.

Abbreviations: NEB = Nebivolol; BBs = Beta blockers; RAM = Ramipril; ACE-is = Angiotensin-converting enzyme inhibitors; SBP = Systolic blood pressure; DBP = Diastolic blood pressure; pts = patients.

## Note:

For the purpose of this study, uncontrolled BP is defined as sitting SBP/DBP ≥130/80 mmHg There is no randomization procedure.

Patients treated with Ramipril or Nebivolol in dosages higher than 5 mg/daily will not be eligible.

- \* Systolic blood pressure ranging from ≥140 to ≤179 mmHg and diastolic blood pressure ranging from ≥90 to ≤109 mmHg.
- \*\* Sitting SBP/DBP  $\geq$ 130/80 mmHg in patients < 65 years old and SBP/DBP  $\geq$  140/80 mmHg in patients  $\geq$  65 years old.

## 3.3. Summary of Change from Planned Analysis

After an Audit conducted by the Sponsor, the Site 114 has been closed for GCP non-compliance due to data quality issues. These data will be cleaned regularly, as for all other sites, but these will

Page 17 of 46

not be included in the Modified Intent-to-Treat (mITT) and Per Protocol (PP) analysis sets. The Sponsor decision process and relevant assessment for the Site closure will be summarized in the Clinical Study Report. To verify the impact of this exclusion on the study results, the primary efficacy analysis will be conducted both with data from site 114 and without data from site 114.

Data from this site will not be excluded from the safety analysis and sensitivity mITT analysis on primary efficacy endpoint (see chapter 16.4).

Moreover, also patients from Site 507 for whom "Primary efficacy source data are unavailable or unreliable" will not be included in the Modified Intent-to-Treat (mITT), as described in the chapters 5 and 16.4

## 4. PLANNED ANALYSES

The following analyses will be performed for this study:

- Final Analysis
- Separate Tables, Listings and Figures for final analysis are documented in TLF\_Shells\_Menarini\_MEIN21AmNe-Hyp001\_Final\_V3.0. TLFs mock shells will be approved along with the SAP approval, and will not be changed without a SAP amendment.
- No interim analysis or analysis for DMC are expected to be executed.

## 4.1. Final Analysis

All final, planned analyses identified in this SAP will be performed by IQVIA Biostatistics following Sponsor Authorization of this Statistical Analysis Plan, Database Lock and Sponsor Authorization of Analysis Sets.

#### 5. ANALYSIS SETS

All population sets for analysis will be discussed with sponsor for statistical analysis during data review meeting and Agreement and authorization of subjects included/excluded from each analysis set will be conducted prior to the database lock of the study.

After an Audit conducted by the Sponsor, the Site 114 has been closed for GCP non-compliance due to data quality issues. These data will be cleaned regularly, as for all other sites, but these will not be included in the Modified Intent-to-Treat (mITT) and Per Protocol (PP) analysis sets. The Sponsor decision process and relevant assessment for the Site closure will be summarized in the Clinical Study Report. To verify the impact of this exclusion on the study results, the primary efficacy analysis will be conducted both with data from site 114 and without data from site 114.

Page 18 of 46

Data from this site will not be excluded from the safety analysis and sensitivity mITT analysis on primary efficacy endpoint (see chapter 16.4).

After two For Cause Audits (one conducted by CRO Indipendent QA Department and the other conducted by the Sponsor), patients from Site 507 for whom "Primary efficacy source data are unavailable or unreliable" will not be included in the Modified Intent-to-Treat (mITT) and so in the Per Protocol (PP) analysis sets. The Sponsor decision process and relevant assessment for the exclusion of these patients will be summarized in the Clinical Study Report. To verify the impact of this exclusion on the study results, the primary efficacy analysis will be conducted both with data from these patients and without data from these patients.

Data from these patients will not be excluded from the safety analysis and sensitivity mITT analysis on primary efficacy endpoint (see chapter 16.4).

## 5.1. All Subjects Enrolled Set [ENR]

The Enrolled (ENR) population will contain Patients who are enrolled into the study (i.e., signed ICF and met the eligibility criteria) and may or may not receive the study treatment (monotherapy and/or combination therapy).

## 5.2. Modified Intent-to-Treat Population [mITT]

The Modified Intent-to-Treat (mITT) population will contain all patients who are in the Enrolled population, receive at least one dose of combination therapy, and have at least baseline (Week 0) and Week 12 assessments with primary efficacy data. Data from Site 114 and data from patients of Site 507 excluded for primary efficacy source data unavailable or unreliable, will not be included in the Modified Intent-to-Treat (mITT) population (see chapter 3.3 and 5).

A sensitivity Modified Intent-to-Treat (mITT) primary endpoint analysis will be conducted for mITT population including all patients (see chapter 16.4).

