12.3 Analysis Populations

In this study, 4 types of analysis population will be used.

- Enrolled population: Patients who are enrolled into the study (i.e., signed ICF and met the eligibility criteria) and may or may not receive the study treatment (monotherapy and/or combination therapy).
- Safety population: Patients who are in the Enrolled population and receive at least 1 dose of monotherapy (either followed by combination therapy or not).
- Modified Intent-to-Treat (mITT) population: Patients who are in the Enrolled population and receive at least 1 dose of combination therapy and have at least baseline (Week 0) and Week 12 assessments with primary efficacy data.
- Per-Protocol (PP) population: All patients included in the mITT population who do not have any major protocol deviations that could affect the primary efficacy analyses.

REVARIN	Glol	pal Medical Department	
	Protocol Template		
Identification Number	Version Number State Effective dat		Effective date
FORM-000050125	3.0, CURRENT	Effective	13 May, 2022

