## 5.4. Per Protocol Analysis Set [PPAS]

All patients included in the mITT population who do not have any major protocol deviations that could affect the primary efficacy analyses.

Page 19 of 46

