## 7.3. Missing Data

All analyses will be performed on observed data. Missing data will not be imputed for this study.

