## 16.1.3. Primary Analysis of Primary Efficacy Variable(s)

The primary objective of this study is to test the hypothesis that

H0: There is no change in the sitting SBP prior or post combination therapy.

H1: There is a difference in the sitting SBP prior or post combination therapy.

The above hypothesis will be tested as following:

Change from baseline in sitting SBP from prior and post combination therapy will be tested using paired t-test. The 2-sided p-value obtained from the paired t-test will be presented.

The primary efficacy analysis will be performed for the mITT population. Site 114 patient data will be removed from the mITT population due to site closure for GCP non-compliance issues. To verify the impact of this exclusion on the study results, the primary efficacy analysis will be conducted both with data from site 114 and without data from site 114.

Page 28 of 46

Assumption of Normality will be investigated using Wilk-Shapiro test. If the p-value is greater than .05, it means we cannot reject the null hypothesis that a variable is normally distributed. If the data is found to be non-Normal, the paired t-test will be replaced by Wilcoxon signed rank test.

The primary endpoint will be summarized descriptively using n, mean, median, SD, Q1, Q3, minimum, and maximum.

Only those patients for whom we have SBP assessment results available at both Baseline (Week 0) and Week 12 will be considered. If baseline (Week 0) SBP value is missing the patient is not included in the mITT population.

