## 16.1.4. Supplementary Analysis of Primary Efficacy Variable(s)

A repeated measure mixed model (MMRM) will be performed on the primary efficacy endpoint to test the covariate effects and the effects of interactions between the covariates for the only mITT population. The MIXED model will include change in mean sitting SBP as the dependent variable, repeated through visits Visit 3 (Week 4), Visit 4 (Week 8) and Visit 5 (Week 12). Age (years), gender, body mass index (BMI), and baseline SBP are considered as the covariates. The MIXED model is

SBP Change from Baseline = Visit + Age + Gender + BMI + baseline SBP + Age\*Gender + Age\*BMI + Age\*baseline SBP + Gender\*BMI + Gender\*baseline SBP + BMI\*baseline SBP + Age\*Gender\*BMI + Age\*Gender\*baseline SBP + Age\*BMI\*baseline SBP + Gender\*BMI\*baseline SBP + Age\*Gender\*BMI\*baseline SBP + Age\*Gender\*BMI\*baseline SBP

A PROC MIXED procedure, with an unstructured covariance matrix, is used for the analysis and the corresponding two-sided p-values for each of the covariates will be presented in a table. If the fit of the unstructured covariance structure fails to converge, the following covariance structures will be tried in order until convergence is reached: Toeplitz with heterogeneity, compound symmetry, autoregressive with heterogeneity, toeplitz, and autoregressive. Smaller value of AIC and BIC will be considered for selection of best fit for covariance structure.

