## 16.2. Secondary Efficacy

Secondary efficacy variables will be analyzed using both the mITT as well as the PP population.

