## 16.4 Sensitivity Analysis Including Data from Site(s) with Data Quality Issues

For Site 114 excluded for data quality issues, sensitivity analysis will be performed including data on the primary efficacy endpoint.

For the patients from Site 507 excluded for primary efficacy source data unavailable or unreliable data, sensitivity analysis will be performed including data on the primary efficacy endpoint.

Variable	Analysis set	Analysis type
Change in mean sitting SBP between Visit 2 (Week 0) and Visit 5 (Week 12)	mITT including all patients (all patients from Site 114 and Site 507)	Paired t-test

In the case of a significant difference between the results of the two primary efficacy analyzes (mITT vs. mITT including all patients), the efficacy outcome (primary, secondary and exploratory) variables will be analyzed using both the mITT as well as the "mITT including all patients" population. All results of the "mITT including all patients" analysis will be reported in the CSR.

Data from Site 114 and from those patients from Site 507 for whom primary efficacy data are unavailable or unreliable will not be excluded from the safety analysis.

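### Every planned Visit 2 to Week 12 efficacy analysis is confined to patients with a Week 12 reading, and the SAP does not settle whether an early-termination Visit 5 counts as Week 12

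*SAP*

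**What the plan says.** Protocol 12.3 defines the mITT set as enrolled patients with at least one combination dose who "have at least baseline (Week 0) and Week 12 assessments with primary efficacy data". SAP 5.2 carries this over, taking enrolled patients who "receive at least one dose of combination therapy, and have at least baseline (Week 0) and Week 12 assessments with primary efficacy data", and SAP 16.1.3 repeats it for the primary test: "Only those patients for whom we have SBP assessment results available at both Baseline (Week 0) and Week 12 will be considered". SAP 7.3 adds: "All analyses will be performed on observed data. Missing data will not be imputed for this study". SAP 16.1.2 gives intercurrent-event handling as not applicable.

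The other efficacy analyses start from the same set:

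- Per-protocol set (SAP 5.4): "All patients included in the mITT population who do not have any major protocol deviations that could affect the primary efficacy analyses".
- MMRM over Visits 3 to 5 (SAP 16.1.4): run "for the only mITT population". It is specified to report covariate p-values; no Week 12 mean is named.
- Secondary endpoints (SAP 16.2): "Secondary efficacy variables will be analyzed using both the mITT as well as the PP population".
- Site sensitivity analysis (SAP 16.4): the set is described as "mITT including all patients (all patients from Site 114 and Site 507". It restores the two sites and does not say that the Week 12 condition is lifted.

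Two groups of tables use wider sets. The exploratory analyses (SAP 16.3.2) use the Enrolled set as well as mITT, and the vital-sign tables (SAP 18.5) use the Safety set.

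On early leavers, Protocol 10 and SAP 9.1 ask them to complete the Visit 5 assessments. SAP 9.1 allows premature withdrawals into any set, subject to how the set is derived. SAP 6.3 uses nominal visits for by-visit summaries and names early discontinuation data only for listings. SAP 6.4 sets a window of ±2 days. Appendix 1 lists Early Termination as a visit apart from Visit 5 (Week 12).

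**The concern.** This is a single-arm before-after trial, so the headline result is the mean SBP change itself, and no control arm would show selection. If patients who stop early did worse than those who stay, the reported fall and goal rates are too favourable; if strong responders leave, they are too unfavourable. Dropout could well be related to response or tolerability: Protocol 10 lists adverse events, laboratory abnormalities and the need for prohibited medication among the reasons for stopping. The planned robustness checks cannot show the direction, because they keep the condition in question.

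The open Week 12 rule adds a second problem. The same early leaver can be inside or outside the primary test depending on how one Visit 5 form is classified. As written, that is left to the data review meeting, in an open-label trial.

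**Working it through.** **1. The plan's own figure.** Protocol 12.2: SD 12.0, difference 5.4 − 3.0 = 2.4 mmHg, one-sided alpha 0.05, power 90%.

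n = [12 × (1.645 + 1.282) / 2.4]² = 214.1, rounded up to **215**, as stated. For screening, 215 / 0.80 = 268.75, so 269 against 270 stated. The 20% combines screen failure and drop-out, so it gives no rate of loss after Visit 2.

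**2. Loss that the cap allows.** Protocol 5 caps entry at 110 per monotherapy arm: 2 × 110 = 220. The target is 215 completers. (220 − 215) / 220 = 5/220 = **2.3%**. This is the largest loss that still meets the target, not a forecast. The higher rates below are assumptions.

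**3. Bias from describing only patients with Week 12 data.** Let p be the share lost, and let patients with Week 12 data change by −5.4 mmHg (the planning value). Then

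overstatement of the fall = p × (leavers' change + 5.4).

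A negative result means that the fall is understated. The last column assumes that 50% of patients with a Visit 5 reading are at goal and that no leaver is: 50% × (1 − p).

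| Loss p | Leavers 0 | Leavers −2.7 | Leavers −10.8 | 50% goal rate becomes |
|---|---|---|---|---|
| 2.3% | 0.12 | 0.06 | −0.12 | 48.9% |
| 5% | 0.27 | 0.14 | −0.27 | 47.5% |
| 10% | 0.54 | 0.27 | −0.54 | 45% |
| 20% | 1.08 | 0.54 | −1.08 | 40% |

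**4. Would an MMRM without the Week 12 condition help?** Simulation with 220 entrants and 3,000 runs. Assumed mean changes were −4, −5 and −5.4 mmHg at Visits 3, 4 and 5, with SD 12 and correlation 0.5 or 0.7. Dropout came after Visit 3 or 4, with log-odds ±1 per 12 mmHg. Absolute bias in mmHg (Monte Carlo error about 0.015):

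| Dropout depends on | Loss | Completers only | MMRM, all treated |
|---|---|---|---|
| Observed Visit 3 or 4 change | 2.3% | 0.12–0.21 | at most 0.02 |
| Observed Visit 3 or 4 change | 10% | 0.57–0.80 | under 0.02 |
| Unobserved Week 12 change | 2.3% | 0.27–0.30 | 0.15–0.20 |
| Unobserved Week 12 change | 10% | 1.11–1.14 | 0.53–0.82 |

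In the unobserved case at 10% loss the MMRM removes only about 27 to 52% of the bias. The standard error is about 0.8 mmHg either way.

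**5. Significance.** Two-sided test against zero, 5.4 mmHg, SD 12: power is above 99.9% at n = 215 and still at n = 220 × 0.80 = 176.

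**6. The Week 12 rule.** Day 1 is the first combination dose (SAP 6.1), so Week 12 is Day 85 and the ±2-day window is Days 83 to 87. Take a patient who withdraws and completes the Visit 5 assessments on Day 40. SAP 9.1 leaves room for that patient in mITT. The window, the confinement of early discontinuation data to listings and the separate Early Termination label suggest otherwise. No sentence says which governs the primary endpoint.

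**The case against.** Four points can be made for the plan.

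*Wider-set tables exist.* The Enrolled-set analyses include between-visit changes in uncontrolled patients and goal rates at Visits 2 to 5 with confidence intervals. SAP 7 even permits the whole analysis population as denominator. This stands as far as it goes: a reader might infer that early leavers vanish from every output, and they do not. But the Enrolled set includes patients never given the combination, its overall changes run from Visit 1, and both it and the Safety set use observed values only. Neither yields the Visit 2 to Week 12 change in patients who started the combination.

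*The visit rules do not contradict one another.* A reader might infer that they do; the documents do not support that. SAP 6.3 names early discontinuation data only for listings. SAP 9.1 is conditional on population derivation. The separate discontinuation summary in SAP 18.5 is ambiguous, because the protocol's schedule labels Visit 5 itself as Week 12/EOT. This objection stands: the rule is unsettled rather than contradictory. Agreeing membership before database lock (SAP 5) does not supply a written rule.

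*The size is mostly assumption.* True. Only the 2.3% follows from the documents; the higher loss rates and the simulation settings do not.

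*An added MMRM is imperfect.* Also true. It cannot include anyone without a reading after Visit 2, and it corrects only for dropout explained by observed readings.

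**Conclusion.** The concern holds in this form: every planned Visit 2 to Week 12 efficacy analysis describes patients with a Week 12 reading, and the rule that decides who has one is not fully written down. For the site sensitivity set this rests on its natural reading, since it is still called mITT.

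The likely effect is modest. At 2.3% loss the bias is about 0.06 to 0.30 mmHg, well below the standard error. At an assumed 10% it is about 0.3 to 1.1 mmHg, against a planned difference of 2.4. The direction is unknown. What is affected is the size of the reported fall and the goal rates. A reader might infer that the primary result could lose significance through this selection; under the planning values it would not. The change should be made, but it is not a fatal flaw.

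**What to change.** 1. Keep the paired t-test on mITT as the primary analysis.
2. Add one sensitivity MMRM on all patients with at least one combination dose, a Visit 2 SBP and at least one later scheduled SBP. Apply the same Site 114 and Site 507 exclusions as mITT, so that only the Week 12 condition differs. Use visit, baseline SBP and main-effect covariates, repeated within patient, with unstructured covariance. Report the Week 12 mean change with 95% CI and the number of treated patients with no later reading. State its two limits: it corrects only for dropout explained by observed readings, and it does not cover patients with no reading after Visit 2.
3. Add a Visit 5 goal-rate sensitivity table on all patients with at least one combination dose, counting those without a Visit 5 blood pressure as not at goal.
4. State one Week 12 rule for mITT and the primary test, covering early-termination and off-window Visit 5 readings, and reconcile SAP 6.3, 6.4, 9.1 and Appendix 1 with it. Treating early-termination readings as not Week 12 fits most of the current text, but the choice is the sponsor's.

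The cost is a SAP amendment before database lock and a few extra tables from data already collected. The sensitivity estimates may come out slightly less favourable. Timing matters: under Protocol 12.7, analyses not prespecified and run after lock count only as additional or exploratory.
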